#### 4. PATIENT SELECTION

This trial will be conducted in compliance with the protocol, GCP and the applicable local regulatory requirement(s).

#### 4.1 Informed Consent

All patients/Legally Acceptable Representatives (LAR; such as a parent or guardian, as applicable) will be asked to sign informed consent to both **Parts I** and **II** separately as applicable. Assent, when appropriate, will be obtained according to institutional guidelines and ICH GCP (E6), FDA, Declaration of Helsinki and the applicable regulatory requirement(s). Telemedical consent will be accepted, if permitted under local regulations and approved by the local governing REB/IRB for **Part I** only.

The patient may also provide consent/assent for future biomedical research. Additionally, the patient may also provide consent/assent for processing of fresh tumour sample (to viable frozen cells, see *Lab Manual*) if sufficient remaining tumour (after all diagnostic and trial-related assays) is available prior to freezing or fixation for possible use during **Part II** if enrolled.

## 4.2 Patient Eligibility

## 4.2.1 Part I - Molecular Profiling Inclusion Criteria

In order to participate in **Part I**, patients must meet the following criteria:

- 1. Consent/ Assent: Patient and/or Legally Acceptable Representative (LAR; such as a parent or guardian, as applicable) must be willing and able to provide written informed consent/assent for the trial as per local requirements.
- 2. Age: patients must be ≥ 12 months and <25 years of age at time of Part I enrollment. Local centres are only obligated to treat/ admit patients in accordance their age range capabilities.
- **3.** Recurrent or relapse paediatric cancer patients suspected to be hypermutant, including those exhibiting evidence of one or more of the following:

- a. high microsatellite instability (MSI-H) in current or previous tumour;
- b. a mutation causing loss of mismatch repair gene (*MLH1*, *MSH2*, *MSH6*, *PMS2*, *EPCAM* or *MSH3*) expression;
- c. hypermutation by local sequencing in current or previous tumour;
- d. a history of CMMRD, Lynch syndrome, xeroderma pigmentosum (XP), or other established disorder associated with an elevated tumour mutation rate;
- e. a functional mutation of polymerase genes (*POLE* or *POLD1*) in current or previous tumour;
- f. a functionally impaired RRD pathway by other means;
- g. a temozolomide (TMZ) treated current or previous CNS tumour;
- h. a predisposing hypermutant cancer signature (i.e. dysregulation of an apolipoprotein B mRNA editing enzyme, catalytic polypeptide-like (APOBEC) cytidine deamination or UV-associated);
- other factors, which may predicate an elevated mutation burden at the discretion of the Study Chair or Co-Chair.
- **4. Diagnosis:** patients must have histologic or cytologic confirmation of malignancy at the time of initial diagnosis or relapse (as specified above). Patients with multiple concurrent and/or sequential neoplasms are eligible, including CNS and haematological malignancies.
- 5. Specimen availability: patients must be able to provide specimen (archival or newly obtained biopsy) of a tumor lesion, appropriately obtained and preserved in a manner compatible for TMB analysis or applicable IHC staining for MMR gene protein expression, if applicable (as described in the *Lab Manual*). Only those with an already ascertained TMB level report from the laboratory specified in the *Lab Manual* or those with proof of RRD as outlined in the *Lab Manual* will be exempt from mandatory tissue submission. If tissue (including archival) is not available, a new tissue specimen may be obtained if deemed clinically appropriate. Any such biopsy will *not* be considered a trial-related procedure.

## 4.2.2 Part II - Treatment and Companion Biomarker Inclusion Criteria

In order to participate in **Part II**, patients must meet the following criteria:

- **1. Consent/ Assent:** Patient and Legally Acceptable Representative (LAR; such as a parent or guardian, as applicable) must be willing and able to provide written informed consent/assent for the trial as per local requirements.
- **2. Confirmation of Hypermutation or Proof of RRD:** patient must have completed and verified a sufficient TMB level or have proof of RRD diagnosed in the appropriate lab, as outlined in the *Lab Manual*.
- 3. Age: patients must be ≥ 12 months and < 25 years of age at the time of Part II enrollment.

  Local centres are only obligated to treat/ admit patients in accordance their age range capabilities.
- **4. Diagnosis:** patients must have had histologic verification of malignancy at the time of initial diagnosis or at relapse (as specified above). Patients with multiple concurrent and/or sequential neoplasms are eligible, including CNS and haematological malignancies.
- **5. Disease status:** patients must have either measurable or evaluable disease in accordance with criteria as outlined in *Section 10*. Tumour lesions situated in a previously irradiated area are considered measurable if progression has been demonstrated in such lesions.
- **6. Treatment options:** patient's current disease state must be one for which there is no known curative therapy or therapy proven to prolong survival with an acceptable quality of life. Chemotherapy-naïve patients will be eligible in cases where first-line therapy does not include chemotherapy (e.g. surgery alone for management of ependymoma).
- 7. Performance status: Karnofsky  $\geq 50\%$  for patients > 16 years of age or Lansky  $\geq 50$  for patients  $\leq 16$  years of age. Patients who are unable to walk because of paralysis, but who are

up in a wheelchair, will be considered ambulatory for the purpose of assessing the performance score.

- **8. Previous treatment:** patients must have fully recovered from the acute toxic effects of all prior anti-cancer therapy.
  - **a. Myelosuppressive chemotherapy:** at least 21 days after the last dose of myelosuppressive chemotherapy (42 days if prior nitrosourea).
  - **b. Hematopoietic growth factors**: at least 14 days after the last dose of a long-acting growth factor (e.g. Neulasta) or 7 days for short-acting growth factor. For agents that have known adverse events occurring beyond 7 days after administration, this period must be extended beyond the time during which adverse events are known to occur. The duration of this interval must be discussed with the Study Chair or Co-Chair.
  - **c. Biologic (anti-neoplastic agent):** at least 14 days after the last dose of a biologic agent. For agents that have known adverse events occurring beyond 14 days after administration, this period must be extended beyond the time during which adverse events are known to occur. The duration of this interval must be discussed with the Study Chair or Co-Chair.
  - **d. Monoclonal antibodies:** at least three (3) half-lives of the antibody after the last dose of a monoclonal antibody.
  - e. Radiation Therapy (XRT): at least 14 days after local palliative XRT (small port). At least 150 days must have elapsed if prior Total Body Irradiation, craniospinal XRT or if ≥ 50% radiation of pelvis. At least 42 days must have elapsed if other substantial BM radiation.
  - **f. Stem Cell Infusion without Total Body Irradiation (TBI):** no evidence of active graft vs. host disease and at least 56 days must have elapsed after transplant or stem cell infusion. Patients with prior allogeneic transplants (including solid organ) are not eligible

## 9. Organ Function Requirements:

- a. Adequate BM Function Defined as
  - i. Peripheral absolute neutrophil count (ANC)  $\geq$ 0.75 x 10^9/L or 750/mm^3.
  - ii. Platelet count ≥75 x 10^9/L or 75,000/mm^3 (transfusion independent, defined as not receiving platelet transfusions for at least 7 days prior to enrollment.

- iii. Hemoglobin  $\geq 90g/L$  (transfusion permitted).
- iv. Patients with known BM metastatic disease or haematological malignancies will be eligible for study provided they meet haematological criteria. These patients may receive transfusions (e.g. to achieve platelet threshold) provided they are not known to be refractory to platelet transfusions but will not be evaluable for hematologic toxicity.

### b. Adequate Renal Function Defined as:

A serum creatinine based on age/gender as provided in *Table 3*.

**Table 3.** The threshold creatinine values in this Table were derived from the Schwartz formula (Schwartz, 1985) for estimating GFR utilizing child length and stature data published by CDC.

Age	Maximum Serum Creatinine			
	Male		Fem	iale
	mg/dL	$\mu mol/L$	mg/dL	$\mu mol/L$
1 to $\leq$ 2 years	0.6	53	0.6	53
2  to < 6  years	0.8	71	0.8	71
6 to < 10 years	1	88	1	88
10 to < 13 years	1.2	106	1.2	106
13 to < 16 years	1.5	133	1.4	124
≥ 16 years	1.7	150	1.4	124

## c. Adequate Liver Function Defined as:

i. Bilirubin (sum of conjugated + unconjugated or total bilirubin)  $\leq 1.5x$  institutional upper limit of normal (ULN) for age (except for patients with Gilbert's Syndrome, when bilirubin of  $\leq 51 \ \mu mol/L$  or  $3.0 \ mg/dL$  is permitted).

#### ii. ALT/AST:

- 1.  $\leq$  2.5 x institutional ULN for patients without liver metastases.
- 2.  $\leq$  5 x institutional ULN for patients with liver metastases.

#### d. Adequate Pulmonary Function Defined as:

No history of chronic pulmonary disease (such as Cystic Fibrosis) and no evidence of dyspnea at rest, no exercise intolerance due to pulmonary insufficiency and a pulse oximetry > 92% on room air.

### e. Adequate Pancreatic Function Defined as:

Serum lipase ≤ ULN. Patients with glucose intolerance should be on a stable regiment and be monitored.

10. For patients with brain tumors, debulking surgery prior to treatment with nivolumab should be considered when appropriate to reduce the risk of pseudoprogression-associated toxicities. Such debulking surgery is not mandatory for trial enrollment. Patients should be recovered from surgery and wait at least 7 days from surgery before first dose.

# 4.2.3 Part II (ONLY) Exclusion Criteria

## 1. Pregnancy or Breastfeeding:

Women who are pregnant or breastfeeding and men who are sexually active with women of child bearing potential (WOCBP)\* who are not willing to use effective contraception, or to practice abstinence if this is the usual lifestyle and preferred contraception for the patient.\*\*

- Pregnant or breastfeeding women will not be entered on this study due to risks of fetal and teratogenic adverse events as there is no available information yet regarding human fetal or teratogenic toxicities.
- Women of childbearing potential (WOCBP)\* must have a negative pregnancy test every 4 weeks. During Part II screening, WOCBP must have a negative serum pregnancy test.
   WOCBP must have a negative serum or urine pregnancy test (minimum sensitivity 25 IU/L or equivalent units of HCG) within 24 hours prior to the start of nivolumab administration.
- WOCBP who are sexually active must be willing to adhere to effective contraception or to
  practice abstinence if this is the usual lifestyle and preferred contraception for the patient\*\*
  during treatment and for 5 months after the last dose of nivolumab.
- Men who are sexually active with WOCBP must be willing to adhere to effective contraception\*\* during treatment and for 7 months after the last dose of the study drug.
- Women who are surgically sterile, as well as azoospermic men, do not require contraception.
  - \* "Women of childbearing potential" is defined as any female who has experienced menarche and who has not undergone surgical sterilization (hysterectomy or bilateral oophorectomy) or who is not postmenopausal.
  - \*\* List of contraception methods is provided in Appendix II.

#### 2. Concomitant Medications

**a.** Corticosteroids: patients requiring systemic steroid therapy or any other form of immunosuppressive therapy within seven (7) days prior to the first dose of trial therapy or while on trial are not eligible. The use of physiologic doses of corticosteroids (up to 5mg/m²/day prednisone equivalent) is permitted following discussion with the Study Chair or Co-Chair.

Note: Use of topical, ocular, intra-articular, intra-nasal or inhaled corticosteroids will not render a patient ineligible. A brief course of corticosteroids for prophylaxis (e.g. contrast dye allergy) or for treatment of non-autoimmune conditions (e.g. delayed-type hypersensitivity reaction caused by contact allergen) is permitted if completed at least 7 days prior to initiation of therapy.

- **b. Investigational Drugs:** patients who are currently receiving another investigational drug are not eligible.
- c. Anti-cancer Agents: patients who are currently receiving other anti-cancer agents are not eligible.

## 3. Patients with a History of Autoimmune Disease:

Patients with a history of autoimmune disorder that has required systemic treatment in the previous 2 years are not eligible. Asymptomatic laboratory abnormalities (e.g. ANA, rheumatoid factor, altered thyroid function studies) will not render a patient ineligible in the absence of a diagnosis of an autoimmune disorder. Replacement therapy (e.g. thyroxine, insulin or physiologic corticosteroid replacement therapy) is not considered a form of systemic treatment.

- **4. Infection:** Patients who have an uncontrolled infection are not eligible.
- **5. HIV and/or Hepatitis B/C patients:** Patients with known HIV/AIDS or acute/chronic Hepatitis B or C are excluded.
- **6. Transplant patients:** patients who have received prior allogeneic BM transplants or prior solid organ transplantation are not eligible.

- 7. **Non-compliance:** patients who in the opinion of the investigator may not be able to comply with the safety monitoring requirements of the study are not eligible.
- **8. Previous anti-PD-1 inhibitor and/or anti-PD-L1 inhibitor therapy:** patients who have received prior anti-PD-1 and/or anti-PD-L1 directed therapy (mAb or small molecule) are not eligible.
- **9. Live vaccines:** Patients who have received a live vaccine within 30 days of start of study treatment are not eligible.

## **4.3** Patient Registration Procedures

Consent to the **Part I** assessment must be obtained prior to sending an existing specimen to the Hospital for Sick Children (Toronto, Canada) or to the specific CLIA-certified laboratory agreed by the Study Chair or Co-chair as outlined in the *Lab Manual*. If tissue (including archival) is not available, a new tissue specimen may be obtained if deemed clinically appropriate. Sites will assign each patient with a patient ID study number during **Part I**. Any such biopsy will *not* be considered a trial-related procedure. Potential patients for whom tumour material (either at diagnosis or relapse) has already been sequenced and analyzed in a specific Study Chair or Co-chair approved and CLIA-certified laboratory reporting evidence of hypermutation may consent directly to **Part II**. In the absence of available specimen necessary for participation in the TMB assay, proof of RRD may confer eligibility (as outlined above and in the *Lab Manual*). An explanation of the study and full disclosure of the informed consent document will take place. Patients or Parents/Legal Guardians will be required to sign the appropriate study consent form for **Part I**.

Once the Part I - Molecular Profiling assays have been completed and patient is verified as eligible for participation in Part II - Treatment and Companion Biomarker Studies, an explanation of the study and discussion of the expected side effects and full disclosure of the informed consent document will take place. Patients or Parents/Legal Guardians will be required to sign the appropriate study consent form for Part II.

Only eligible and consented patients will be registered into the study. Registration will be done through *Ozmosis Research Inc*.

Prior to registering a patient, each institution must have submitted all necessary regulatory documentation to *Ozmosis Research Inc.* Access to the eCRFs will only be granted once this documentation has been received. Prior to enrolling a new patient, sites should contact *Ozmosis Research Inc.* to verify study availability.

No patient can receive protocol treatment until eligibility has been confirmed and the Patient Enrollment Form has been submitted to and acknowledged by *Ozmosis Research Inc*. All eligibility criteria must be met at the time of registration. There will be no exceptions. Any questions should be addressed with *Ozmosis Research Inc*. and/or the Study Chair or Co-Chair prior to registration.

The Patient Enrollment Form must be completed, and signed by the investigator prior to enrollment. This form can be faxed to (+1) [contact] or emailed to [contact]. There are four (4) sections to the 'Patient Enrollment Form':

- 1. SCREENING PART I (top section): This section is completed by the site and should be sent to *Ozmosis Research Inc.* at the time of screening into Part I. This section must be completed for all Part I screened patients, including screen failures.
- 2. ENROLLMENT PART I: This section is completed by the site and should be sent to Ozmosis Research Inc. at the time of enrollment into Part I.
- **3. SCREENING PART II**: This section is completed by the site and should be sent to *Ozmosis Research Inc.* at the time of screening for **Part II**.
- **4. ENROLLMENT PART II** (bottom section): This section is completed by the site and should be sent to *Ozmosis Research Inc.* at the time of patient registration/enrollment to **Part II**.

Protocol treatment should begin within 14 days of patient enrollment to **Part II**. All eligible patients enrolled into either part of the study will be entered into a patient registration log at *Ozmosis Research Inc*.

The following information will be required at the time of registration:

- Trial code;
- Treatment centre and investigator;
- Patient's month and year of birth;

• Completed Patient Enrollment Form.

N.B.: It is the responsibility of the investigator in charge to satisfy him or herself that the patient is indeed eligible before requesting registration.

#### 5. TREATMENT PROGRAM

#### 5.1 Treatment Plan

All eligible patients will receive nivolumab in the dose of 3 mg/kg every 14 days (2 weeks). Each cycle of therapy will last for 28 days (4 weeks) total, therefore two (2) doses will be administer per cycle, if the patient has not met any of the criteria for removal from therapy. A maximum length of the therapy on this study is 24 months (see *Figure 2*).

[figure not shown]

Figure 2. Nivolumab treatment cycle and evaluation plan.

\*See Section 8.2 for required disease evaluations. Therapy will be discontinued if there is evidence of confirmed progressive disease (PD) or drug related toxicity that requires removal from therapy.

Nivolumab will be administered as a 60-minute  $\pm$  10-minute infusion. Infusion rate may be slowed as per physician's discretion as clinically indicated (see *Section 6.3*).

The dosing calculations should be based on the actual body weight in kilograms and may be calculated using the weight obtained at the previous dose administration. If the patient's weight on the day and prior to drug administration differs by >10% from the weight used to calculate the dose, the dose should be recalculated. All doses should be rounded to the nearest milligram. There will be no dose modifications allowed.

Pre-medication is not required as infusion reactions are rare, but anaphylactic precautions should be observed during each infusion of nivolumab. If  $\geq$  Grade 2 infusion reaction occurs, the infusion should be stopped and supportive care given as per institutional guidelines. See *Section* 6.3 for management and dose modification guidelines for infusion reactions.

During the Cycle 1 Day 1 initial drug administration, investigators are advised to monitor vital signs (see *Section 8.2* for details) and watch for adverse events (AE) such as, fever, chills, shakes, itching, rash, hypertension or hypotension, difficulty breathing and so on beginning at baseline, then every 15 minutes (+/- 5 min.) during administration of the drug. After the completion of the nivolumab infusion, the patient should continue to be monitored every 15 minutes (+/- 5 min.) twice, then every 30 minutes (+/- 5 min.) three (3) times. Following completion of cycle 1

and in patients who have tolerated nivolumab without infusion reactions, frequency of vital sign evaluation following infusion may be reduced at the discretion of, and documented by, the treating physician.

## **5.2** Criteria for Starting Subsequent Cycles

A cycle, consisting of two (2) doses every 14 days +/- 2 days, may be repeated every 28 days if the patient has not met any of the criteria for removal from therapy.\*

## Nivolumab administration should be delayed for the following:

- 1. Any Grade  $\geq$  2 non-skin, drug-related AE, with the following exceptions:
  - Grade 2 drug-related fatigue or laboratory abnormalities do not require a treatment delay;
  - Any Grade 3 skin, drug-related AE.
- 2. Any Grade 3 drug-related laboratory abnormality except for the following exceptions:
  - Grade 3 lymphopenia or leukopenia does not require dose delay;
  - If a patient has a baseline AST, ALT, or total bilirubin that is within normal limits, delay dosing for drug-related Grade ≥ 2 toxicity;
  - If a patient has baseline AST, ALT, or total bilirubin within the Grade 1 toxicity range, delay dosing for drug-related Grade ≥ 3 toxicity;
  - Grade ≥ 3 drug-related amylase or lipase abnormality that is not associated with symptoms or clinical manifestations of pancreatitis does not require dose delay, but requires close follow-up.
- 3. Any AE, laboratory abnormality or intercurrent illness, which, in the judgment of the investigator, warrants delaying the dose of study medication.

\* Patients who require delay of nivolumab should be re-evaluated weekly or more frequently if clinically indicated and resume nivolumab dosing when re-treatment criteria are met (see Section 5.3 for details).

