## 6.4 Dose Modifications for Skin Rash and Oral Lesions

Skin Rash and	Management/Next Dose of Nivolumab
Oral Lesions	
≤ Grade 1	No change in dose*
Grade 2	
 
Continue protocol therapy.*
 
Topical steroids do not require protocol therapydiscontinuation. If prolonged symptoms require systemic corticosteroids, decisions regarding whether protocol therapymay be reinstituted following weaning of immunosuppression must be made in consultation with Study Chair or Co-Chair.
 

Grade 3	
 
Hold* until ≤ Grade 1; if resolves within seven (7) days, then resume at same dose level.
 
Topical steroids do not require protocol therapydiscontinuation. If prolonged symptoms require systemic corticosteroids, decisions regarding whether protocol therapymay be reinstituted following weaning of immunosuppression must be made in consultation with Study Chair or Co-Chair.
 

Grade 4	Discontinue therapy, systemic corticosteroids indicated.

\*Patients with purpuric or bullous lesions must be evaluated for vasculitis, Steven-Johnson syndrome (SJS), toxic epidermal necrolysis (TEN), and autoimmune bullous disease including oral lesions of bullous pemphigus/pemphigoid. Pruritus may occur with or without skin rash and should be treated symptomatically if there is no associated liver or GI toxicity.

Note: Skin rash typically occurs early and may be followed by additional events particularly during steroids tapering.

**Recommended management:** See Skin AE Management Algorithm (Section 6.4.1).

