# 6.4.1 Recommended Skin Adverse Event Management Algorithm

Toxicity	Management	Follow-up
(CTCAE v.4.03)		
Grade 1-2 Rash: Covering ≤ 30% BSA*	
 
Symptomatic therapy (e.g. antihistamines, topical steroids);
 
Continue protocol therapyas per protocol.
 
	
 
If persists >1-2 weeks or recurs:
 
Consider skin biopsy;
 
Hold protocol therapy;
 
Consider 0.5-1.0 mg/kg/day         Methylprednisolone IV or oral         equivalent;
 
Once improving, taper steroids         over at least 1 month;
 
Consider prophylactic antibiotics         for opportunistic infections
 
Then resume nivolumab therapy         per protocol.
 
If worsens:
 
Treat as Grade 3-4.
 

Grade 3-4	Hold or discontinue therapy	If improves to Grade 1:
Rash: Covering	as per protocol'	• Taper steroids over at least 1
> 30% BSA; life	• Consider skin biopsy;	month;
threatening	• Dermatology consult;	Add prophylactic antibiotics for
consequences*^	• 1.0 – 2.0 mg/kg/day	opportunistic infections
	methylprednisolone IV or IV equivalent.	
 
Resume nivolumab therapy as per protocol.
 

Patients on IV steroids may be switched to an equivalent dose of oral corticosteroids (e.g. prednisone) at start of tapering or earlier, once sustained clinical improvement is observed. Lower bioavailability of oral corticosteroids should be considered when switching to the equivalent dose of oral corticosteroids.

'If Stevens-Johnson syndrome (SJS)/ toxic epidermal necrolysis (TEN) is suspected, withhold nivolumab therapy and refer patient for specialized care for assessment and treatment. If SJS or TEN is diagnosed, permanently discontinue nivolumab therapy.

\*Refer o NCI CTCAE v.4.03 for term specific grading criteria.

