## 7.4 Skin Related Toxicity

For skin-related Grade 3 autoimmune toxicity lasting > 7 days or Grade 4 autoimmune toxicity, including severe generalized pruritus or rash, symptomatic treatment will be given, and patients will be removed from protocol therapy. Therapy will be as clinically indicated and may include local skin care, antihistamines, or corticosteroids (which can be local/topical or systemic). The use of topical corticosteroids for grades 1-3 dermatitis will be allowed, and will not require patients to be removed from study. In the case of late-occurring hypersensitivity symptoms (e.g., appearance within one week after treatment of a localized or generalized pruritus), symptomatic treatment may be given (e.g., oral antihistamine, topical steroids for the skin).

A dermatologist should evaluate persistent (lasting greater than seven (7) days) and/or severe rashes or pruritus. Patients should be advised to seek medical evaluation if they notice new-onset rash. Early consultation with a dermatology specialist and a biopsy should be considered if there is uncertainty as to the cause of the rash, or if there is any unusual appearance or clinical feature associated with it. Other drugs that may cause rash should be considered in the differential and, if possible, discontinued. A biopsy should be performed if appropriate and photos should be obtained.

If symptoms or signs of SJS or TEN appear, nivolumab should be withheld and the patient should be referred for specialized care for assessment and treatment. If the patient has confirmed SJS or TEN, permanent discontinuation of nivolumab is mandatory.

Please refer to *Sections 6.4 and 6.4.1* for dose modification and management of the skin toxicities.

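### Section 5.2 lists Grade 3 drug-related skin events as an exception to a delay rule that covers only non-skin events, so the dosing list is incoherent on them and conflicts with the hold in Sections 6.4 and 6.4.1

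*Protocol*

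**What the plan says.** The list in Section 5.2 opens with "Nivolumab administration should be delayed for the following" and has three numbered items.

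- **Item 1** covers drug-related events of Grade 2 or higher, restricted to "non-skin, drug-related AE, with the following exceptions". Two unnumbered bullets follow. The first is "Grade 2 drug-related fatigue or laboratory abnormalities do not require a treatment delay". The second is "Any Grade 3 skin, drug-related AE", with no statement of what to do.
- **Item 2** covers Grade 3 drug-related laboratory abnormalities and has its own list of exceptions.
- **Item 3** lets the investigator delay for any event, abnormality or illness on judgment.

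Elsewhere the protocol deals with Grade 3 skin events as follows.

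- **Section 6.4**, Grade 3 row for skin rash and oral lesions: "Hold* until ≤ Grade 1; if resolves within seven (7) days, then resume at same dose level".
- **Section 6.4.1**, Grade 3-4 rash: "Hold or discontinue therapy".
- **Section 5.3** allows dosing to resume with Grade 2 skin toxicity still present, but only in patients who have not had a Grade 3 drug-related skin event.
- **Section 6.2** spares from removal a Grade 3 rash or oral lesion that settles to Grade 1 or lower within seven days.
- **Section 7.4** sets removal from protocol therapy, opening "For skin-related Grade 3 autoimmune toxicity lasting > 7 days" and adding Grade 4.

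**The concern.** Section 5.2 is the operative list that decides whether the next dose is given or delayed. If its only entry on skin toxicity appears as an exception to delaying, a site that works from the list alone could treat a Grade 3 skin event as no bar to dosing. A site that works from the skin table would hold.

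Patient safety comes first. There is also a consequence for the data. The study is multi-centre (Section 3.1.1), and safety and tolerability form a secondary objective (Section 2.2). If two sites handle the same event differently, exposure after that event differs for reasons unrelated to the patient. Protocol deviations also become hard to classify: on the exemption reading, a site that doses complies with 5.2 and departs from 6.4, and a site that holds does the reverse. Whether a delay is started matters further because Sections 5.3 and 6.2 both attach discontinuation or removal to the length of a delay.

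**Working it through.** No arithmetic applies. The point depends on no sample size, error rate or event rate, so the check is a comparison of the texts.

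**Step 1: is the bullet really inside the exceptions?** The items of the list run 1, 2, 3 in sequence. The skin entry has no number and comes directly after the fatigue and laboratory bullet, under the exceptions wording of item 1. The unbroken numbering makes an error in reading the PDF an unlikely explanation.

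**Step 2: what does the bullet mean there?** Two readings are open.

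| Reading | Result for a Grade 3 skin event | Difficulty |
|---|---|---|
| It is an exception, like the bullet before it | Exempt from delay | The parent rule excludes skin events, so there is nothing to exempt |
| It is a delay trigger misplaced under item 1 | Delay | It stands under wording that says the opposite and carries no number |

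The text of 5.2 does not decide between them. The first reading follows the position of the bullet. The second fits the heading of the list and the fact that, unlike the other no-delay bullets in 5.2, this one does not say that no delay is needed.

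**Step 3: does anything else in 5.2 settle it?** Item 1 is limited to non-skin events. Item 2 concerns laboratory values. Only item 3 can reach a Grade 3 skin event, and it is discretionary. The bullet is therefore the only skin entry in the list.

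**Step 4: compare with the other sections.**

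| Section | Event covered | Instruction |
|---|---|---|
| 5.2, item 1 bullet | Any Grade 3 drug-related skin event | Exempt, or no coherent instruction |
| 5.3 | Previous Grade 3 drug-related skin event | Stricter condition for resuming, which presupposes an interruption |
| 6.4 | Grade 3 rash and oral lesions | Hold |
| 6.4.1 | Grade 3-4 rash | Hold or discontinue |
| 6.2 | Grade 3 rash or oral lesions | Not removed if settled within seven days |
| 7.4 | Grade 3 autoimmune skin toxicity beyond 7 days, or Grade 4 | Removal |

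The conflict lies between 5.2 on one side and 5.3, 6.4 and 6.4.1 on the other. Sections 6.2 and 7.4 concern removal, which is a different decision from delaying the next dose.

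**Step 5: how far does the conflict reach?** Section 5.2 speaks of any skin event, Section 6.4 of rash and oral lesions, and Section 6.4.1 of rash. The demonstrable overlap is rash and oral lesions.

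**Step 6: look at item 2.** Two liver-test bullets stand under exceptions wording and yet direct a delay: from Grade 2 where the baseline is normal, and from Grade 3 where the baseline is in the Grade 1 range. They are awkwardly placed, but each states its action, so a site knows what to do.

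**The case against.** The best defence is that no careful site would be misled. The parent rule never covered skin events, so an exception for one removes nothing, and the entry looks like a delay trigger that lost its number. Section 5.3, to which 5.2 refers the reader, assumes that a Grade 3 skin event interrupts dosing. Sections 6.4 and 6.4.1 call for a hold or more, Section 6.2 adds a removal rule, and item 3 allows a delay in any case. To dose through an ongoing Grade 3 rash, a site would have to adopt an incoherent reading of one bullet and pass over several other sections.

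Much of this stands. It limits the practical risk, and it rules out four stronger conclusions that a reader might draw:

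- **That the protocol plainly permits dosing through a Grade 3 skin event.** The bullet is incoherent where it stands, which falls short of a clear permission.
- **That item 2 has the same fault.** Its liver-test bullets state their action outright, so they cannot be read as exempting anything from delay.
- **That Section 7.4 is a second contradiction.** Removal after a period of persistence can coexist with either rule on delaying the next dose.
- **That every Grade 3 skin event is caught.** Sections 6.4 and 6.4.1 are narrower than the bullet, so the conflict is shown only for rash and oral lesions.

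The defence does not remove the fault itself. The list used to decide on a dose should not need four other sections to make sense of its only skin entry, and item 3 substitutes judgment for a rule that other sections state firmly.

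**Conclusion.** The point holds in a limited form. The only skin entry in Section 5.2 stands as an exception to a rule that does not cover skin events. It therefore reads either as an exemption from delay or as no instruction, and both conflict with the hold in Section 6.4, the hold or discontinuation in Section 6.4.1 and the interruption that Section 5.3 presupposes.

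The conflict is established for Grade 3 rash and oral lesions. How often it would arise cannot be stated, because the protocol gives no expected rate of such events. That sites would in fact diverge is a possibility and is not shown; many would infer a hold. The conclusion rests on one assumption, that the bullet structure of the list as read is that of the protocol, which the numbering supports. It takes no position on which clinical rule should apply.

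Because the list governs dosing and the repair is nearly free, it should be corrected even though the practical risk is limited.

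**What to change.** The sponsor should reconcile Section 5.2 with Sections 5.3, 6.4 and 6.4.1, and check that 6.2 and 7.4 remain consistent with the result. Section 5.2 should then state once, as its own numbered item outside the exceptions, whether a Grade 3 drug-related skin event delays dosing. It should also say whether that item covers all skin events or only rash and oral lesions, so that its scope can be matched to 6.4. Merely deleting the bullet would not do, since 5.2 would then say nothing about skin events apart from investigator judgment.

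As a secondary tidy-up, the liver-test bullets in item 2 can be moved out from under the exceptions wording. Their substance is not in question here.

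The cost is re-formatting and wording in one list, with a consistency check of the sections named. No design parameter or sample size changes.
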